# **5.4.3** Rationale for Staggering Intervals

All participants in Cohort 1a – those who receive Treg supportive IS alone - must be monitored for 12 weeks prior to enrollment of Cohort 2 and Cohort 1B by the second clinical site. The rationale for selecting 12 weeks is that this interval covers the time period that has the highest incidence of important post-liver transplant complications such as rejection and infection, particularly bacterial and fungal infections related to the transplant operation including those directly related to the transplant incision / wound.

Within each darTreg dosing cohort, there is a mandatory four-week observation period after the administration of darTregs to the 1st patient of each cohort before the 2nd patient can receive darTregs. We have selected a shorter observation time interval for several reasons. First, darTregs will be administered sometime between Week 11-20 after transplant. This is a period of relative clinical quiescence that will readily permit optimal identification of AEs that may be precipitated by the darTreg infusion. Liver transplant recipients have largely recovered from the transplant operation as well as from the baseline liver disease. They continue on anti-viral (until 6 months after transplantation) and anti-

Confidential Page 40 of 80

pneumocystis prophylaxis (until at least 12 months after transplantation) such that the frequency of these infections is very low. Second, we anticipate that the majority of complications associated with darTreg administration (infusion reaction, AR, or infection) are most likely to occur early, soon after administration while the beneficial effect of darTreg administration may well evolve and/or intensify over time. Infection may be precipitated by contamination of the darTreg preparation with infectious agents or with non-donor-alloantigen-reactive Tregs that lead to generalized over-immunosuppression. Similarly, rejection may be precipitated by contamination of the darTreg preparation with T effector cells. In these cases, the deleterious impact of darTreg infusion is expected to manifest soon – within 4 weeks – after infusion. While malignant transformation of infused cells is a concern, the timeframe of this complication as well as its manner of presentation is certainly difficult if not impossible to predict and therefore, this safety concern cannot be mitigated by any sort of mandatory waiting period.

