#### 15.4.2 Analysis of Safety Outcomes

As the safety outcomes are all person-week incidence rates of selected AEs as described in *Section 3.2*, they will be estimated using proportions and exact two-sided 95% confidence intervals in the Safety Sample as a whole and within the two analysis periods defined above.

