2.2 Safety Objective

This study will evaluate the safety, tolerability, and dose limiting toxicities (DLT's) of a Treg-supportive IS regimen and darTreg infusion for adult, de novo, liver transplant recipients.

3. Sample Size Considerations

This pilot study is designed to evaluate 18 subjects through Stage 3 in a modified 3+3 dose escalation design. Therefore, no formal power and sample size analysis have been performed. However, with 18 evaluable subjects undergoing darTreg supportive IS for 12 weeks of follow-up (6 subjects for 40 weeks of follow-up) and up to 12 evaluable subjects undergoing darTreg infusions for 28 weeks of follow-up, exact 95% confidence intervals on person-week incidence rates will vary in width by analysis period. For example, the following table (**Table 1**) shows incidence rates and confidence intervals for selected numbers of events and person-weeks of 216 (18 subjects x 12 weeks), 336 (12 subjects x 28 weeks), and 384 (6 subjects X 40 weeks and 12 subjects X 12 weeks) in the two analysis periods. It is not known at this time how many subjects may be expected to comprise the entire Safety Sample.

Table 1. Incidence Rates and Confidence Intervals for Selected Numbers of Events and Person-Weeks

Number of Events	Total Person-Weeks	Person-Weeks Incidence Rate	Lower 95% Confidence Limit	Upper 95% Confidence Limit
2	216	0.0093	0.0011	0.0334
4	216	0.0185	0.0050	0.0474
6	216	0.0278	0.0102	0.0605
8	216	0.0370	0.0160	0.0730
10	216	0.0463	0.0222	0.0851
12	216	0.0556	0.0287	0.0970
14	216	0.0648	0.0354	0.1087
16	216	0.0741	0.0423	0.1203
18	216	0.0833	0.0494	0.1317
20	216	0.0926	0.0566	0.1430
2	336	0.0060	0.0007	0.0215
4	336	0.0119	0.0032	0.0305
6	336	0.0179	0.0066	0.0389
8	336	0.0238	0.0103	0.0469

10	336	0.0298	0.0143	0.0547
12	336	0.0357	0.0185	0.0624
14	336	0.0417	0.0228	0.0699
16	336	0.0476	0.0272	0.0773
18	336	0.0536	0.0317	0.0847
20	336	0.0595	0.0364	0.0919
<hr/>				
2	384	0.0052	0.0006	0.0188
4	384	0.0104	0.0028	0.0267
6	384	0.0156	0.0057	0.0340
8	384	0.0208	0.0090	0.0410
10	384	0.0260	0.0125	0.0479
12	384	0.0313	0.0161	0.0546
14	384	0.0365	0.0199	0.0612
16	384	0.0417	0.0238	0.0677
18	384	0.0469	0.0278	0.0741
20	384	0.0521	0.0318	0.0804

4. General analysis and reporting conventions

The following analyses and reporting conventions will be used:

- Categorical variables will be summarized using counts (n) and percentages (%) and will be presented in the form n (%). Percentages will be rounded to one decimal place.

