8.1.1 Safety Outcome Analyses

The safety outcomes will be considered in two ways: the absolute number and the person-week incidence rates (*Section 3.2*) of selected adverse events following transplantation. The person-week incidence rate will be estimated using proportions and exact binomial two-sided 95% confidence intervals for the Safety Sample as a whole and within the two analysis periods defined above. The absolute number and the estimated incidence proportions of the following will be reported:

- Biopsy-proven acute and/or chronic rejection
- Grade ≥ 3 infections as defined in Section 13.3.1 of the Protocol
- Wound complications (\geq CTCAE Grade 3)
- Anemia, neutropenia, and/or thrombocytopenia (\geq CTCAE Grade 3)
- Adverse events attributable to the darTreg infusion including infusion reaction/cytokine releaser syndrome (\geq CTCAE Grade 3), and malignant cellular transformation.

Descriptive statistics will also be presented for:

- The severity of biopsy-proven acute and/or chronic rejection
- Reasons for termination of subjects who did not receive leukapheresis
- Use of concomitant medications

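### Infusion reaction/CRS is a one-time risk per infusion, but the plan summarises it per person-week, in one line with malignant transformation, and no planned estimate clearly uses infused subjects as denominator

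*SAP*

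**What the plan says.** SAP 8.1.1 sets the summary measures for all five safety outcomes: "The safety outcomes will be considered in two ways: the absolute number and the person-week incidence rates". It then says that "The person-week incidence rate will be estimated using proportions and exact binomial two-sided 95% confidence intervals for the Safety Sample as a whole", and also within the two analysis periods. The fifth outcome is "Adverse events attributable to the darTreg infusion including infusion reaction/cytokine releaser syndrome" at CTCAE grade 3 or higher, and malignant cellular transformation stands in the same line. Protocol 15.4.2 has the same approach: "As the safety outcomes are all person-week incidence rates of selected AEs".

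Under SAP section 5, weeks at risk in the darTreg period start at the infusion and run to the end of the subject's follow-up. SAP section 3 plans "up to 12 evaluable subjects undergoing darTreg infusions for 28 weeks of follow-up", which is 336 person-weeks.

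Protocol 3.1 and 5.1.2 give each subject a single infusion. Protocol 5.4.3 names infusion reaction, acute rejection and infection as complications likely to come early. For infection or rejection caused by a contaminated product, it says that "the deleterious impact of darTreg infusion is expected to manifest soon", within 4 weeks. The same section treats the timing of malignant transformation as close to unpredictable.

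**The concern.** A person-week rate is a natural summary when the hazard is roughly constant while a subject is under observation. An infusion reaction is not like that. There is one opportunity per subject, and later weeks add to the denominator but cannot add events. Malignant transformation is the opposite case: its timing is unknown and length of observation matters. One rate for both describes neither.

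This is the product-specific safety outcome for a cell product that Protocol 1.4 says has not been used in humans. Whoever plans the next trial will want the risk per infusion and its uncertainty. What is at stake is whether the planned output states that figure or leaves readers to rebuild it.

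**Working it through.** **Reproducing the plan's own figure.** SAP Table 1 (identical to Protocol Table 8) gives 0.0060 (0.0007 to 0.0215) for 2 events in 336 person-weeks. With k events in T person-weeks the rate is k/T. The exact Poisson limits are χ²(0.025; 2k)/(2T) and χ²(0.975; 2k+2)/(2T). For k = 2 and T = 336 they give 0.0060 (0.0007 to 0.0215), as printed, and all 30 rows of the table reproduce. Exact binomial limits with person-weeks as n give 0.0007 to 0.0213 for this row and match none of the 30 rows on both limits. So the table is exact Poisson although the SAP 8.1.1 text says exact binomial.

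**Inputs.** 12 infused subjects and 28 weeks each (SAP section 3); 384 person-weeks on supportive immunosuppression = 6 × 40 + 12 × 12 (same section); infusion at weeks 11 to 20 after transplant (Protocol 10.4). Assumption: no dropout.

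**Per infusion against per person-week.** Clopper-Pearson limits for k of n are the 0.025 quantile of Beta(k, n−k+1) and the 0.975 quantile of Beta(k+1, n−k). The rate uses T = 12 × 28 = 336.

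| Reactions | Per infused subject, n = 12 | Per person-week, T = 336 |
|---|---|---|
| 0 | 0% (0 to 26.5%) | 0 (0 to 0.0110) |
| 1 | 8.3% (0.2 to 38.5%) | 0.0030 (0.0001 to 0.0166) |
| 2 | 16.7% (2.1 to 48.4%) | 0.0060 (0.0007 to 0.0215) |

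The two scales differ by the number of weeks followed, here 28. If Cohorts 2 and 3 each expand to 6, n = 18 and one reaction is 5.6% (0.1 to 27.3%), against 1/504 = 0.0020 per person-week.

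**Whole Safety Sample.** Planned person-weeks are 384 + 336 = 720, so one reaction is 1/720 = 0.0014. Of that time, 384/720 = 53% lies before infusion or in Cohort 1, which is never infused. Multiplying back by 28 weeks gives 28/720 = 3.9%, not 8.3%, so this figure cannot be converted to a per-infusion risk without the split by period. Any person-time from subjects who had only leukapheresis would lower it further.

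**SAP 9.2 percentages.** These are based on the number of subjects in the analysis population. With 6 never-infused and 12 infused subjects, one reaction would be 1/18 = 5.6% overall, and less once subjects who had only leukapheresis are counted. The rates in 9.2 use person-time from enrolment.

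**Infusion week.** SAP sections 2 and 2.1 follow subjects to week 40 after transplant. Protocol 10.7 and Appendix 3 place the last visit 28 weeks after infusion, and Protocol 10.4 gives both end points. The two agree only for infusion at week 12. Taking all 12 subjects infused in the same week:

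| Infusion week | Person-weeks to week 40 | Rate, 1 event | Person-weeks, 28 weeks after infusion | Rate, 1 event |
|---|---|---|---|---|
| 11 | 12 × 29 = 348 | 0.0029 | 336 | 0.0030 |
| 12 | 12 × 28 = 336 | 0.0030 | 336 | 0.0030 |
| 20 | 12 × 20 = 240 | 0.0042 | 336 | 0.0030 |

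Under the week-40 end point the largest ratio is 348/240 = 1.45, with the per-infusion risk unchanged at 8.3%. Under the other end point there is no change.

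**The case against.** The strongest reply is that little is lost. SAP 8.1.1 also reports the absolute number. With one infusion per subject and about 12 infused, a reader can form x/12 at once. The same paragraph mentions estimated incidence proportions and binomial intervals, so one reading of the text is already close to what is asked for here. The fifth outcome is an open category of attributable events, not a strict two-part composite, and later attributable events give a reason to follow it beyond the first days. SAP 9.2 tabulates subjects by preferred term, cohort and stage, which separates reactions from malignancy, and SAP 9.3 has its own malignancy display. The analyses are descriptive, and the holds in Protocol 14.8.1 act on absolute counts, so no trial decision uses the rate.

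Most of this stands: it makes the point one of clear reporting. It does not remove the point. The incidence proportions are not tied to infused subjects, and the worked table uses person-weeks. The 9.2 percentages have the analysis population as denominator and no interval. SAP 9.3 has no display for infusion reaction/CRS.

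Three stronger readings are tempting. A reader might infer that the rate must change with the infusion date; the documents support that only under the week-40 end point. A reader might compare 336 person-weeks with the 48 (12 × 4) in the first 4 weeks and infer a 7-fold understatement of early risk; that assumes every event falls in those weeks, whereas Protocol 5.4.3 says only that most are likely to be early. A reader might also infer that dose escalation or stopping is compromised; the stopping thresholds are counts, so it is not.

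**Conclusion.** The point holds as a matter of interpretability. The plan's main estimate for infusion reaction/CRS is a person-week rate that includes weeks in which the event cannot occur, and in the whole Safety Sample 53% of planned person-time could never yield it. One reaction in 12 infusions, 8.3% (0.2 to 38.5%), would be shown as about 0.0030 or 0.0014 per person-week. The numerator is recoverable from other outputs, but the per-infusion estimate with its interval is not clearly planned anywhere. The dependence on infusion week, up to 1.45-fold, is conditional on which end of follow-up applies and on the extreme contrast of all subjects at week 11 against all at week 20.

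The figures assume 12 infused subjects, no dropout and the planned follow-up times. With "no formal power and sample size analysis have been performed" and a descriptive analysis, no error rate or trial decision is affected. This is a cheap improvement, not a flaw in the design.

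**What to change.** In SAP 8.1.1, with matching wording in Protocol 15.4.2:

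- Report grade 3 or higher infusion reaction/CRS on its own line, as subjects affected over subjects who started a darTreg infusion, overall and by dose cohort, with Clopper-Pearson 95% limits.
- Report malignant transformation on a separate line, as a count with person-time. Any other attributable events can stay as planned.
- Reconcile the two end points of follow-up for infused subjects (40 weeks after transplant and 28 weeks after infusion), so that person-time in the darTreg period has one definition.

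The cost is a few lines of SAP text and slightly more table work, with no new data. The intervals will be wide: one reaction is 0.2 to 38.5% with 12 infused and 0.1 to 27.3% with 18. By cohort, one reaction in 3 is 33.3% (0.8 to 90.6%) and one in 6 is 16.7% (0.4 to 64.1%). That width reflects what a trial of this size can say.

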9. ADDITIONAL SAFETY EVALUATIONS

9.1 Overview of Safety Analysis Methods

All safety analysis will be carried out using the safety sample defined in Section 5 above unless otherwise noted. Missing safety information will not be imputed. Safety will be analyzed through the reporting of adverse events, vital signs, physical examinations, and changes in routine laboratory values.

9.2 Adverse Events

All adverse events will be classified by system organ class and preferred term, according to a standardized thesaurus (MedDRA version 17.0). The severity of AEs will be classified using the National Cancer Institute's Common Toxicity Criteria for Adverse Events, with the exception of infections which will be graded according to protocol definitions.

An overall summary table will be developed to report the number of events and the number and percentage of subjects having at least one event in the following categories:

- AEs
- AEs indicated as serious (SAEs)
- AEs that lead to study discontinuation
- AEs with an outcome of death
- AEs reported by maximum severity

In addition, adverse events classified by MedDRA system organ class and preferred term will be summarized for each study cohort and overall for each of the following:

- All AEs
- AEs by maximum severity
- AEs by study stage

The summary tables will present the total number of events as well as the number and percentage of subjects experiencing the events. When reporting the number of AEs, if the same AE occurs for a subject on multiple occasions the event will be counted once for each occurrence. When reporting the number of subjects experiencing the events, a subject will only be counted once if they ever experience an event within the particular system organ class or preferred term. Percentages will be based on the number of subjects in the analysis population.

A summary table of incidence rates adverse events classified by system organ class and MedDRA preferred term will be provided. Incidence rate for a system organ class or preferred term will be defined as the number of adverse events divided by the person-time since the subject enrolled.

Separate data listings will be provided for AEs leading to study discontinuation.

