# 10. Study Visits

# 10.1 Stage 1: Screening, Enrollment and PBMC Collection

The first stage of the study encompasses screening A and enrollment. Participants will be selected from the liver transplant waiting lists according to the study eligibility criteria (Screen A). The research study will be explained in lay terms to each potential research participant by the site PI or designee listed on FDA form 1572. The potential participant will sign an informed consent form before undergoing any screening or study procedures. Surrogate consent will not be permitted. Once the informed consent form has been signed, the participant will be assigned a unique participant number. All screening procedures will be completed to ensure that the subject meets inclusion criteria and exclusion criteria A (Section 4.2 and 4.3.1).

Eligible and consented participants enrolled in Cohort 2, 3, or 4 will undergo leukapheresis (or blood draw option for Cohort 2) at any time prior to transplantation to isolate PBMCs, which will be cryopreserved for subsequent Treg purification and expansion. Participants who have detectable HBV DNA at the time of PBMC collection will be terminated from the trial. At the time of transplantation, donor material for these participants will be collected to make donor sBcs and banked to support future expansion of darTregs.

At the time of transplantation, participants will receive Solumedrol, 500 mg intravenously. Within 24 hours after transplantation, participants will be started on MMF in the form of either Cellcept 500mg bid intravenously or orally or Myfortic 360 mg bid by mouth. Within 72 hours after transplantation, participants will be prescribed tacrolimus to target 12-hour trough levels of  $6-8~\mu g/L$ . Please refer to *Appendix 1. Recipient Schedule of Events (Stages 1 and 2)*. Note that collection of AEs and SAEs in Stage 1 are limited to events occurring within 72 hours after leukapheresis.

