### 14.4 Collection and Recording of Adverse Events

#### 14.4.1 Collection Period

During Stage 1, AEs will be collected from the time of first study procedure (leukapheresis or 450-500 ml blood draw), until 72 hours after completion of the leukapheresis procedure or 450-500 ml blood draw. AEs occurring outside the 72 hour window should be reported if the investigator deems a possible association with the protocol mandated leukapheresis or blood draw.

During Stages 2 and 3 (including Cohort 1 follow up), AEs will be collected from the time of first Thymoglobulin® administration, until a subject completes study participation or until 30 days after he/she prematurely withdraws (without withdrawing consent) or is withdrawn from the study.

Additionally, elevated liver tests (i.e. ALT, AST, ALP, GGT, and bilirubin) must be reported starting 7 days after transplant. Events involving unexpected elevations of liver tests in the first week should be reported according the site investigator's judgment.

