# 15.6 Sample Size Considerations

This pilot study is designed to evaluate 18 subjects through Stage 3 in a modified 3+3 dose escalation design. Therefore, no formal power and sample size analyses have been performed. However, with 18 evaluable subjects undergoing darTreg supportive IS for 12 weeks of follow-up (6 subjects for 40 weeks of follow-up) and up to 12 evaluable subjects undergoing darTreg infusions for 28 weeks of follow-up after infusion, exact 95% confidence intervals on person-week incidence rates will vary in width by analysis period. For example, the following table (*Table 8. Incidence Rates and Confidence Intervals for Selected Numbers of Events and Person-Weeks*) shows incidence rates and confidence intervals for selected numbers of events and person-weeks of 216 (18 subjects x 12 weeks), 336 (12 subjects x 28 weeks), and 384 (6 subjects x 40 weeks + 12 subjects x 12 weeks) in the two analysis periods. It is not known at this time how many subjects may be expected to comprise the entire Safety Sample, which includes subjects who only received leukapheresis.

Confidential Page 65 of 80

Table 8. Incidence Rates and Confidence Intervals for Selected Numbers of Events and Person-Weeks

Number of	Total Person-	Person-Weeks	Lower 95%	Upper 95% Confidence
Events	Weeks	Incidence Rate	Confidence Limit	Limit
2	216	0.0093	0.0011	0.0334
4	216	0.0185	0.0050	0.0474
6	216	0.0278	0.0102	0.0605
8	216	0.0370	0.0160	0.0730
10	216	0.0463	0.0222	0.0851
12	216	0.0556	0.0287	0.0970
14	216	0.0648	0.0354	0.1087
16	216	0.0741	0.0423	0.1203
18	216	0.0833	0.0494	0.1317
20	216	0.0926	0.0566	0.1430
2	336	0.0060	0.0007	0.0215
4	336	0.0119	0.0032	0.0305
6	336	0.0179	0.0066	0.0389
8	336	0.0238	0.0103	0.0469
10	336	0.0298	0.0143	0.0547
12	336	0.0357	0.0185	0.0624
14	336	0.0417	0.0228	0.0699
16	336	0.0476	0.0272	0.0773
18	336	0.0536	0.0317	0.0847
20	336	0.0595	0.0364	0.0919
2	384	0.0052	0.0006	0.0188
4	384	0.0104	0.0028	0.0267
6	384	0.0156	0.0057	0.0340
8	384	0.0208	0.0090	0.0410
10	384	0.0260	0.0125	0.0479
12	384	0.0313	0.0161	0.0546
14	384	0.0365	0.0199	0.0612
16	384	0.0417	0.0238	0.0677
18	384	0.0469	0.0278	0.0741
20	384	0.0521	0.0318	0.0804

Confidential Page 66 of 80

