PBMC Collection Visit does not apply to Cohort 1. Cohort 2 can have whole blood collection for PBMC isolation if hemoglobin is ≥10.5 mg/dl; leukapheresis if <10.5 mg/dl.

<sup>2 Screening for eligibility C1 and C2 can be assessed between 5-6 weeks (30-44 days) after transplantation. Everolimus can be started on or after 30 days after liver transplantation if eligibility criteria are met (Screen C1).

 $^3\mbox{HIV/HBV/HCV}$  serology can be within one year of screening.

<sup>4AFP is only required for subjects known to have HCC. At Screen A, AFP should be drawn if unavailable within 3 preceding months; AFP should be redrawn at time of transplant. After transplant, AFP should be recorded every 3 months.

<sup>5 First EVR level should be obtained within one week of first dose (+/- 2 days). MMF discontinuation and TAC trough 3-5 μg/L for subjects converting to EVR only. Subjects continuing on TAC-based IS should have troughs 6-8 μg/L.

<sup>6 Prior to Thymoglobulin, collect AE's/SAE's occurring within 72 hours after PBMC Collection only. Collect all AE's/SAE's grade 2 and higher from the time of first Thymoglobulin infusion.

<sup>7 Central laboratory assessments may be drawn up to one year BEFORE solumedrol dose in OR. Once drawn, mechanistic labs do not need to be repeated.

<sup>8CBC, Basic Chemistry, Liver Function Tests, and PT/INR/PTT should be collected as close to, but prior to transplant as possible.

<sup>9Liver allograft biopsy should be obtained prior to transplantation (back table) for local pathology reading only, no specimen for central pathology

<sup>10 Screening should take place within 24 hours prior to Thymoglobulin®. The first dose of Thymoglobulin® is to be given within 72 hours after transplantation. Additional doses of 0.75-1.5 mg/kg IV will be administered until CD3 count is ≤50 cells/μL (50 cells/mcL) or total lymphocyte count is ≤ 0.10 x 10 ½L; or when maximum dose of 4.5/mg/kg has been given. Day 2 and Day 6 visits are only needed if Thymoglobulin is given on these days.

 Treg expansion should be initiated 2-3 weeks prior to planned Treg infusion if subjects continue to meet eligibility criteria. Please refer to Stage 3 Schedule of Events. .

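### SAP 9.2 counts person-time from enrolment, so waiting-list time with little adverse event collection lowers the rates for events after Thymoglobulin in that one descriptive table

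*SAP*

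**What the plan says.** SAP 9.2 plans one table of AE incidence rates by system organ class and preferred term. The rate is "the number of adverse events divided by the person-time since the subject enrolled". No end of person-time is given, and no other section redefines this denominator. SAP 9.1 sets the population: "All safety analysis will be carried out using the safety sample defined in Section 5 above unless otherwise noted". Protocol 15.6 describes that sample as one "which includes subjects who only received leukapheresis", and SAP 5 agrees by counting leukapheresis as study therapy.

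Protocol 10.1 puts enrolment in Stage 1, before transplantation: "Participants will be selected from the liver transplant waiting lists according to the study eligibility criteria (Screen A").

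The rules for AE collection before and after the first Thymoglobulin dose differ:

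- Appendix 1, footnote 6: "Prior to Thymoglobulin, collect AE's/SAE's occurring within 72 hours after PBMC Collection only".
- Protocol 14.4.1 adds that "AEs occurring outside the 72 hour window should be reported if the investigator deems a possible association" with the collection procedure.
- Appendix 1, footnote 1: "PBMC Collection Visit does not apply to Cohort 1".
- Protocol 14.3.1 also records grade changes between screening and baseline as AEs that are not treatment-emergent. It does not define baseline.
- Routine collection starts later, under protocol 14.4.1: "During Stages 2 and 3 (including Cohort 1 follow up), AEs will be collected from the time of first Thymoglobulin® administration".

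**The concern.** A person-time rate is interpretable when the time in the denominator is time during which an event would have been recorded. From enrolment to first Thymoglobulin most events would not be recorded, yet that time is counted. Rates for events that arise after Thymoglobulin are therefore diluted by an amount that depends on how long subjects waited for a liver, which says nothing about the study treatment.

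This is the only planned table that gives person-time rates for all AEs by system organ class and preferred term, and the cell product has not been used in humans before (protocol 1.4). Rates that are too low could be quoted as reassurance or set beside rates from studies that start the clock at treatment.

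**Working it through.** **Step 1. Numerator against denominator.**

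| Interval | In the SAP 9.2 denominator? | AEs collected? |
|---|---|---|
| Enrolment to first Thymoglobulin, Cohort 1 | Yes | No PBMC visit; only any screening-to-baseline grade changes |
| Enrolment to first Thymoglobulin, Cohorts 2-4 | Yes | PBMC collection to 72 hours afterwards, later events possibly associated, any screening-to-baseline grade changes |
| Waiting time of leukapheresis-only subjects | Yes | As for Cohorts 2-4 |
| First Thymoglobulin onwards | Yes | Routine collection |

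The direction for events arising after Thymoglobulin follows from this table: the extra time cannot add to their count.

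**Step 2. The plan's own person-weeks.** SAP Table 1 (Protocol Table 8) uses 6×40 + 12×12 = 384 person-weeks on supportive immunosuppression and 12×28 = 336 after infusion. For 20 events in 384 person-weeks the plan gives 0.0521 (0.0318 to 0.0804). I reproduce this as 20/384, with exact Poisson limits χ²(0.025; 40)/(2×384) and χ²(0.975; 42)/(2×384). All 30 rows of the table agree to rounding. The plan gives no figure for the SAP 9.2 table itself.

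Together, 384 + 336 = 720 = 18×40 person-weeks after transplant. Thymoglobulin starts within 72 hours of transplant (protocol 10.2). Post-transplant time therefore stands in for time since first dose to within 3/280 days, or about 1%.

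**Step 3. Dilution.** Let W be the mean wait in weeks from enrolment to transplant. It is an assumption, because the documents give none. The reported rate divided by the rate over post-transplant time is

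T / (T + 18W),

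with T = 720 if every subject has 40 weeks. Protocol 10.4 allows infusion up to week 20 and schedules visits to 28 weeks after infusion, which would reach week 48. If all 12 infused subjects ran to week 48, T = 6×40 + 12×48 = 816.

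| W assumed (weeks) | T = 720 | T = 816 |
|---|---|---|
| 4 | 720/792 = 0.91 | 816/888 = 0.92 |
| 13 | 720/954 = 0.75 | 816/1050 = 0.78 |
| 26 | 720/1188 = 0.61 | 816/1284 = 0.64 |

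For example, 20 events give 20/720 = 0.0278 per person-week over post-transplant time. With W = 26 they give 20/1188 = 0.0168.

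**Step 4. What moves these factors.**

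- Counting the 72-hour window as observed time in 12 subjects adds 12×3/7 = 5.1 person-weeks and raises each factor in the 720 column by less than 0.01.
- Leukapheresis-only subjects lower the factor. Six of them (an assumed number), each waiting 26 weeks, give 720/(720 + 24×26) = 720/1344 = 0.54.
- The 26 weeks is not a cap. It borrows the six-month Screen A window in Protocol Table 3, whose reference event is not stated. At W = 52 the factor would be 720/1656 = 0.43.

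**The case against.** The strongest reply is that little depends on this table. It is descriptive, and SAP 9.2 also plans AE counts by study stage, from which a reader can separate Stage 1 from later events. SAP 8.1.1 ties its safety outcomes to events after transplantation, and SAP 5 pairs events with weeks at risk in each treatment period. All of this stands and limits the weight of the point.

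Three further objections narrow the claim:

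- A reader might infer that Cohort 1 has no AE collection at all before Thymoglobulin. The documents do not support that. Protocol 14.3.1 records screening-to-baseline grade changes as AEs, although Appendix 1 limits collection before Thymoglobulin to the PBMC window and the two are not reconciled. With baseline undefined, the extent of this source is open. It qualifies the dilution but does not remove it.
- A reader might infer that every rate in the table is too low. That holds for events arising after Thymoglobulin. Terms driven by the PBMC procedure have events in Stage 1 and need not follow the pattern.
- The size depends on an assumed wait and on a fixed 40 weeks that the visit schedule does not guarantee. This is correct, and the factors are illustrations only.

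Separate reporting of the PBMC stage is also not a new idea: protocol 15.4.1 already defines a subset of subjects with PBMCs collected. SAP 5 does not carry it over.

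**Conclusion.** The point holds and is minor. As written, the SAP 9.2 denominator includes waiting-list time with little AE collection, so rates for events arising after Thymoglobulin are too low in this one descriptive table. The direction is firm for those events. The size cannot be fixed from the documents; the illustrative factors run from about 0.9 at an assumed 4-week mean wait to about 0.6 at 26 weeks.

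A reader might go further and infer that the trial's main safety rates or its safety monitoring are biased. The documents do not support this. Event counts, subject percentages, by-stage tables and the analysis-period rates of SAP 5 and 8.1.1 do not use this denominator. The stopping rules in protocol 14.8.1 are absolute event numbers.

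**What to change.** In SAP 9.2, define the rate as the number of AEs with onset on or after the first Thymoglobulin dose, divided by person-time from that dose to the end of AE collection for that subject.

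Report all AEs before first Thymoglobulin separately as counts. These are the PBMC-procedure events, including later ones judged possibly associated, and any screening-to-baseline grade changes under protocol 14.3.1. Use the PBMC-collection subset of protocol 15.4.1 for the procedure events, so that leukapheresis-only subjects stay reported and no recorded event is lost.

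Footnote the terms whose reporting starts later than first Thymoglobulin: liver-test elevations (from day 7 after transplant, protocol 14.4.1) and lymphocyte or CD4 decreases (reporting not required within six months of the last Thymoglobulin dose, protocol 14.3.1). If SAE rates are tabulated under SAP 9.3, which follows 9.2, use the same definition.

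The cost is one redefined rate, one separate display and one footnote. The rate needs the first Thymoglobulin date and the last date of AE collection for each subject. Rates for events after Thymoglobulin will rise. Terms driven by the PBMC procedure may fall, because those events move to the separate counts.
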